6.3.5 Early Termination

Subjects can decide to discontinue entirely from the study at any time for any reason, this is documented as withdrawal of consent. Subjects can decide to discontinue from the study treatment at any time for any reason, but may choose to remain in the study for off-treatment study visits. Subjects can also be discontinued from the study or discontinued from the study treatment due to Investigator or Sponsor decision as detailed below.

The Sponsor or their representative must be notified by the Investigator as soon as possible, and prior to the early termination visit, on the decision to discontinue the subject from the study or from study treatment and provide detailed information on the reason/event.

In case of discontinuation of the subject from the study, a study termination visit (outlined as an End of Treatment visit in the Schedule of Activities) is required immediately and the site must complete the End of Study eCRF data. In case of the discontinuation of the subject from the study treatment, the subject is required to complete the End of Treatment visit, switch to marketed treatment (both basal and bolus treatments) and agree to proceed with the scheduled visits/activities.

The reason for discontinuation should be established based on the criteria for discontinuation/early termination as stated in [Section 4.2.3](#).

Subjects who decide to discontinue from treatment and agree to remain in the study, on marketed treatment, are required to adhere to the study protocol, thus perform all activities and procedures such as SMBG measurements, completing diary entries, participating in their regularly scheduled study visits for completion of all assessments and procedures as outlined in the Schedule of Activities until the Week 28 (Follow-up visit).

If the subject withdraws from the study and also withdraws consent for disclosure of future information, no further evaluations should be performed and no additional data should be collected. The Sponsor may retain and continue to use any data collected before such withdrawal of consent.

The site should explain the subject the importance of data collection and make every effort to consent the subject to continue follow up per the SCHEDULE OF ACTIVITIES until Week 28 (Follow-up visit).

6.4 Visit 16 Follow up (Week 28) (telephone call)

- Discuss and check compliance to standard of care specifics as per American Diabetes Association 2019 guidelines, self-management of diabetes and life-style modifications with the subject.
- Record AEs, SAEs, local and systemic allergic reactions and hypoglycemic episodes
- Record concomitant medications since previous visit

6.5 Treatment Procedures

Every effort should be made to ensure that the protocol required tests and procedures are completed as described. However, it is anticipated that from time to time there may be circumstances, outside of the control of the Investigator that may make it unfeasible to perform the test. In these cases, the Investigator or designated representative will take all steps necessary to ensure the safety and well-being of the subject. When a protocol required test cannot be performed the Investigator or designated representative will document the reason for this and any corrective and preventive actions which he/she has taken to ensure that normal processes are adhered to as soon as possible. The Mylan study team will be informed of these incidents in a timely fashion.

Activities specific to this protocol are expanded upon further below.

6.5.1 Blood Volume

Total blood sampling volume for an individual subject is approximately 375 mL.

Table 3: Blood Volume

Sample Type	Sample Volume (mL)	Number of Sampling Times		Total Volume (mL)
		Screening	Study Period	
Safety Labs	30	1	2	90
FPG, HbA1c	5	2	10	60
Anti-drug antibody (ADA) ¹	10	1	8	90
Neutralizing antibody (NAb) ²	5	1	8	45
Supplemental Immunogenicity ³	10	1	8	90
TOTAL				375

¹ Blood samples (2 x 5 mL) will be drawn into serum separator tubes (SST).

² Blood samples (1 x 5 mL) will be drawn into serum separator tubes (SST).

³ Blood samples (2 x 5 mL) will be drawn into serum separator tubes (SST).

6.5.2 Safety Testing Assessments

Safety will be assessed through physical examinations, monitoring of vital signs, 12-lead electrocardiograms, laboratory analyses, and adverse event monitoring.

6.5.2.1 Adverse Event Assessment

If a subject reports any symptoms after the signing of the informed consent form, they will be evaluated by medical staff and necessary measurements will be performed. The Principal Investigator or Medical Sub-Investigator will be notified before dosing to determine the course of action.

Clinically relevant findings from screening procedures, e.g., laboratory tests or physical examinations will be recorded as medical history. Clinically significant changes from the screening procedures results will be recorded as adverse events.

Subjects will be routinely queried with regard to the presence or absence of adverse events using open ended questions. The clinic will provide documentation of any adverse events in the subject's CRF. The adverse event source documentation will minimally include the

following information: date and time of assessment, the outcome of the response, and identification of the clinic staff member collecting the information.

6.5.2.2 Hypoglycemia

Incidence of hypoglycemic episodes will also be summarized by category (Severe Hypoglycemia, Documented Symptomatic Hypoglycemia, Asymptomatic Hypoglycemia, Probable Symptomatic Hypoglycemia, Relative Hypoglycemia and Nocturnal Hypoglycemia). In addition, nocturnal hypoglycemia rate and incidence will be analyzed in same way as overall hypoglycemic episodes.

Hypoglycemia is a state produced by a lower than normal level of glucose in the blood. This may develop, if for example:

- The subject misses or delays meals or there is a change in diet
- The subject takes a higher dose of study drug than prescribed
- The subject consumes alcohol
- The subject does more intense or longer physical exercise or work than normal,
- The subject is recovering from an injury, operation, fever or other illness, or from other forms of stress

6.5.2.2.1 Classification

A. Severe Hypoglycemia

An event is considered as severe hypoglycemia if it requires the assistance of another person to actively administer carbohydrate, glucagon, or other resuscitative actions which results in neurological recovery, regardless of the availability of a blood glucose measurement. These episodes may be associated with sufficient neuroglycopenia to induce seizure or coma. Plasma glucose measurements may not be available during such an event, but neurological recovery attributable to the restoration of normal plasma glucose is considered sufficient evidence that the event was induced by a low plasma glucose concentration.

B. Documented Symptomatic Hypoglycemia

An event during which typical symptoms of hypoglycemia are accompanied by a measured plasma glucose concentration ≤ 70 mg/dL (3.9 mmol/L).

C. Asymptomatic Hypoglycemia

An event not accompanied by typical symptoms of hypoglycemia but with a measured plasma glucose concentration ≤ 70 mg/dL (3.9 mmol/L).

D. Probable Symptomatic Hypoglycemia.

Characteristic symptoms of hypoglycemia with no blood glucose level measurement that resolved with food intake, subcutaneous glucagon, or intravenous glucose.

E. Relative Hypoglycemia.

An event during which the subject reports any of the typical symptoms of hypoglycemia, and interprets the symptoms as indicative of hypoglycemia, but with a measured plasma glucose concentration > 70 mg/dL (3.9 mmol/L).

F. Nocturnal Hypoglycemia.

Nocturnal hypoglycemia will include hypoglycemia that occurs from the time the subject goes to bed at night till the time he or she wakes up. This may include any of the above 5 types of hypoglycemia.

Note: A diagnosis of severe hypoglycemia as per above classification will always be considered as serious adverse event. Other hypoglycemic episodes which fulfill ICH criteria for seriousness (life-threatening, hospitalization etc.) or represent important medical events based on Investigator's judgment should also be reported to the Sponsor within 24 hours.

6.5.2.2 Identification of Hypoglycemia

Symptoms of hypoglycemia include but are not limited to the following: palpitations, sweating, hunger, nervousness and shakiness, perspiration, dizziness or light-headedness, sleepiness, confusion, difficulty speaking, feeling anxious or weak. Neuroglycopenic manifestations may include seizure, coma, and even death.

Subject will be instructed to be alert for signs and symptoms of hypoglycemia; and if possible to take glucose meter readings at the time of the episode and to record the details of the episode with any remedial action taken and the blood glucose level (if it was checked) in their diary.

Investigators will instruct the subjects on self-management of hypoglycemic episodes. Investigators will instruct subjects on remedial actions to be taken during the episodes of severe hypoglycemia. Subject will be encouraged to call the study site if they experience hypoglycemia.

6.5.2.2.3 Management of Hypoglycemia

The following steps are recommended for managing hypoglycemic episodes:

1. The subject should begin with 15 to 20 grams carbohydrate (e.g., 3-4 teaspoons of table sugar dissolved in water, 1 tablespoon of honey, $\frac{3}{4}$ cup of juice or regular soft drink, 3-4 glucose tablets).
2. Subsequently, if the glucose level is ≤ 50 mg/dL, then the subject will be asked to consume 20 to 30 grams carbohydrate (e.g., 4-6 teaspoons of table sugar dissolved in water, 2 tablespoons of honey, $\frac{3}{4}$ cup of juice or regular soft drink, 4-5 glucose tablets).
3. Subject will be asked to recheck blood glucose after 15 minutes and to repeat hypoglycemia treatment if the blood glucose does not return to normal after 15 minutes. If the next meal is more than 1 hour away, subjects should follow with additional carbohydrate or a snack.
4. If hypoglycemia persists after the second treatment, subject or companion should be instructed to contact the Investigator.

It is recommended that the subjects always carry some sugar lumps, sweets, biscuits, or sugary fruit juice.

For an event of severe hypoglycemia, the subject can be treated with glucagon (0.5 to 1 mg) given intramuscularly or subcutaneously by a person who has received appropriate training, or glucose given intravenously by a medical professional. Intravenous glucose can also be given if the subject does not respond to glucagon within 10 to 15 minutes. Upon regaining consciousness administration of oral carbohydrate is recommended in order to prevent a relapse.

Full hypoglycemic episode documentation includes time of occurrence, duration, time of recovery, remedial measures undertaken, recording the symptoms and plasma glucose / SMBG levels at the beginning and end of the episode with time and date, and classification in to the different subtypes (Refer to [Section 6.5.2.2.1](#)).

6.5.2.2.4 Reporting of Hypoglycemic Episodes

Hypoglycemic events and any associated symptoms are recorded in the diary and reported on the hypoglycemic episodes page of the CRF. Severe hypoglycemia and those episodes meeting any of the ICH seriousness criteria ([Section 9.2.4](#)) are also to be notified as SAEs to the Mylan Global Product Safety and Risk Management department, as described in [Section 9.3.2.8](#); and entered on the SAE and AE pages.

6.5.2.3 Laboratory Safety

The following safety laboratory tests will be performed at times defined in the study schedules in [Section 1](#) and [Section 6](#).

Table 4: Laboratory Safety Tests

Hematology	Chemistry	Urinalysis	Other
Hemoglobin	Urea and Creatinine	pH	Urine/Serum hCG
Hematocrit	Glucose	Glucose (qual)	HIV and HBsAg and
RBC count	Calcium	Protein (qual)	HCVAb
Platelet count	Sodium	Blood (qual)	HbA1c
WBC count	Potassium	Ketones	
Total neutrophils (Abs)	Chloride	Nitrites	
Eosinophils (Abs)	AST, ALT	Leukocyte esterase	
Monocytes (Abs)	Total Bilirubin	Microscopy/culture ⁰	
Basophils (Abs)	Direct/Indirect bilirubin		
Lymphocytes (Abs)	Alkaline phosphatase		
	Uric acid		
	Albumin		
	Total protein		
	CRP		
	C-Peptide		
	Lipid Profile		

^a Only if urine dipstick is positive for blood, protein, nitrites or leukocyte esterase.

Hematology and chemistry will be analyzed by the central laboratory. Urinalysis will be conducted by dipstick at site and if urine is positive for blood, protein, nitrites, or leukocyte esterase, will be analyzed via microscopy/culture by the central laboratory.

Blood volumes to be collected and blood and urine sample handling instructions will be provided in the central vendor laboratory manual. The central laboratory will provide collection materials and directions for packaging and shipment of samples.

Per schedule of activities in [Table 1](#) and [Section 6](#), study conduct, samples are taken under fasting conditions, as described in the laboratory manual. Patients are required to adhere to those requirements/instruction.

Any clinically significant findings in laboratory safety data should be recorded as an AE. Determination of clinical significance and seriousness will be based on the Investigator's medical judgment.

6.5.2.4 Immunogenicity Assessment

Blood samples (5 mL each) will be taken into serum separator tubes at each time point as outlined in [Table 3](#). At Visits 1, 6, 8, 9, 10, 11, 12, 13 and 15, five (5) blood samples of 5 mL each (25 mL total volume) will be drawn. The blood samples will be taken pre-dose by direct venipuncture, and the exact times of blood sampling will be recorded in the CRF. Two of the samples will be used to determine the presence of ADA against insulin aspart using the approach outlined below. One sample will be used to determine the presence of NAb against insulin aspart for samples that are ADA positive. Two samples will be collected and stored in reserve for potential supplemental immunogenicity testing and/or characterization including titer assessment if needed. Samples collected pre-dose at the randomization visit (Visit 6) will be considered as baseline. Samples collected at screening and the supplemental samples collected at baseline may also be used for method development and validation. Sample handling, processing, and storage instructions will be detailed in a separate laboratory manual.

A conventional radioimmunoprecipitation assay (RIPA) will be employed for the assessment of ADA in clinical samples. In this assay, samples will undergo a pre-treatment step that includes acid dissociation to release any anti-insulin antibodies complexed with free drug, followed by charcoal adsorption of the free insulin analog. The treated samples will be incubated with a fixed amount of ^{125}I -MYL-1601D tracer under conditions specified for each tier:

Screening Assay (Tier 1):

- RIPA Assay buffer only

Confirmatory Assay (Tier 2):

- RIPA Assay buffer only
- RIPA Assay buffer with excess unlabelled MYL-1601D
- RIPA Assay buffer with excess unlabelled Human Insulin
- RIPA Assay buffer with excess unlabelled NovoLog

Titer assay (Tier 3)

- RIPA Assay buffer only (multiple serial dilutions of the sample)

Anti-drug antibody complex formation with the tracer is measured via gamma counter and expressed as a percentage of bound to total radioactivity (%B/T).

In keeping with the multi-tiered sample analysis recommendations for immunogenicity testing from published white papers ([Mire-Sluis AR et al, 2004](#); [Shankar G et al, 2008](#)), and

current regulatory guidance ([FDA 2019](#), [EMA 2017](#)), the assay design will employ a screening tier (no inhibition), confirmatory tier (competitive inhibition with excess drug), characterization tier (competitive inhibition with excess human insulin and excess NovoLog®) and titration tier.

All samples will be subjected to an initial screening assay (Tier 1), and those with %B/T values greater than or equal to a run-specific screening cut point will be scored as putative ADA positives.

Screen positive samples would then undergo the confirmatory assay (Tier 2), and samples exhibiting percentage inhibition greater than the confirmatory cut point will be scored as confirmed positive. The cut-point for the screening assay will be based on the %B/T response using normal human serum from treatment naïve individuals and use a 5% false positive error rate. The confirmatory cut points will be determined for both ADA and insulin cross-reactive ADA based on the % inhibition of tracer binding using excess MYL-1601D and human insulin, respectively. Each confirmatory cut-point will be determined using normal human serum from treatment naïve individuals and employ a 1% false positive error rate. The percent inhibition determined using NovoLog as inhibitor would be reported for comparison purposes.

All confirmed positive samples will be evaluated for titer (Tier 3) by serially diluting the samples (2-fold dilution steps) and estimating the titer as the interpolated dilution at the run specific titer cut point (determined from the screening data using normal human serum from treatment naïve individuals at 0.1% false positive error rate). In addition, all samples identified as ADA positive will be further evaluated for neutralizing antibodies using a separate cell-based assay.

The labeled drug product (^{125}I -MYL-1601D) is used as the capture reagent in the RIPA, which allows antibodies that arise from any insulin aspart epitope to be bound and detected. The specificity of capture reagent binding is confirmed by treatment with excess unlabeled MYL-1601D, which will interrupt binding for any of the insulin aspart epitopes. Because this assessment theoretically detects all antibodies that may arise due to drug exposure, it will be used to determine patient sample ADA status.

Since endogenous human insulin possesses close sequence homology to insulin aspart, the ADA generated upon drug exposure may also cross react with human insulin. The degree of cross reactivity will be determined by testing the sample in the presences of excess human insulin. ADA that develop against epitopes common to both insulin aspart and human insulin will be inhibited from binding to the capture reagent.

All samples designated for immunogenicity evaluation will be tested in a blinded manner. The ADA and NAb analysis methodologies will be fully validated at Celerion Switzerland AG (Zurich, CH) and Cirion BioPharma Research Inc. (Quebec, CA), respectively, followed by sample analysis.

6.5.2.5 Blood Pressure and Pulse Rate

Blood pressure and pulse rate will be measured at times specified in [Section 1](#) and [Section 6](#). Additional collection times, or changes to collection times of blood pressure and pulse rate will be permitted, as necessary, to ensure appropriate collection of safety data.

Blood pressure will be measured at sitting position, after 5 minutes rest.

The same size blood pressure cuff, which has been properly sized and calibrated, will be used to measure blood pressure each time. The use of automated devices for measuring blood pressure and pulse rate are acceptable, although, when done manually, pulse rate will be measured in the brachial/radial artery for at least 30 seconds. Any clinically significant changes in blood pressure and pulse rate should be recorded as an AE. Determination of clinical significance and seriousness will be based on the Investigator's medical judgment.

6.5.2.6 12-lead ECG

In this study, 12-lead ECGs will be recorded using local ECG devices and review. ECGs should be collected at times specified in the study schedules in [Section 1](#) and [Section 6](#).

All scheduled ECGs should be performed after the subject has rested quietly for at least 5 minutes in a supine position.

To ensure safety of the subjects, a medically qualified individual at the site will assess ECG recordings and make any comparisons to baseline measurements.

In some cases, it may be appropriate to repeat abnormal ECGs to rule out improper lead placement as contributing to the ECG abnormality. It is important that leads are placed in the same positions each time in order to achieve precise ECG recordings. Any clinically significant ECG abnormalities measured at screening should be assessed for their effects on subject eligibility of the study and recorded in medical history. ECG parameters will not be recorded in the CRFs, but any clinical significant changes between the screening and subsequent ECGs should be recorded as an AE. Determination of clinical significance and seriousness will be based on the Investigator's medical judgment.

6.5.2.7 Diary and Glucometer

All subjects will receive a diary and blood glucose monitoring (glucometer) device at Visit 2/Week -4. The glucometer device will be used by the subject at home to monitor blood glucose and the diary will be used to record the 7-point SMBGs. The Investigator or designee will train subjects on how to use the glucometer and how to record the values and required information in the diary. A user manual for the glucometer is provided to each site as a tool to educate and train both site personnel and study subjects.

6.5.2.8 General Physical Examination

A full general physical examination will consist of an examination of the abdomen, cardiovascular system, lungs, lymph nodes, musculoskeletal and neurological systems, skin, extremities, head, ears, eyes, nose, and thyroid gland by trained medical personnel at the site. A full physical examination will be performed at Visit 1 (screening), Visit 6 (randomization) and Visit 15 (EOT).

Height and weight will be assessed at Visit 1. Physical examination results will not be recorded in the CRFs, but any clinical significant finding at Screening (Visit 1) should be recorded under medical history and changes between Screening (Visit 1) and subsequent examinations should be recorded as an AE. Determination of clinical significance and seriousness will be based on the Investigator's medical judgment.

7 STATISTICAL ANALYSIS

Detailed methodology for summary and statistical analyses of the data collected in this study will be documented in a Statistical Analysis Plan (SAP), which will be dated and maintained by the Sponsor. This document may modify the plans outlined in the protocol; however, any major modifications of the primary endpoint definition and/or its analysis will also be reflected in a protocol amendment.

7.1 Sample Size Determination

Approximately 500 subjects with type 1 diabetes will participate in this trial. The sample size estimation is based on primary objective - to demonstrate that immunogenicity as assessed by TEAR rate with MYL-1601D is equivalent to that of NovoLog® during 24-week treatment. The 80% power will be achieved with 250 subjects per treatment arm to demonstrate that 90% confidence interval of treatment difference (MYL-1601D minus NovoLog®) is within prespecified \pm margin (Table 5). (Chow SC et al, 2002; Chow S-C et al, 2003). The pre-specified equivalent margin is dependent on the final rate of NovoLog® TEAR rate. No replacement of subject will be performed if subject discontinued prematurely from the study. An attrition rate is not considered; for the analysis an imputation of missing values will be done and no patient will be excluded from the primary analysis.

Table 5: Margins and 95% CIs with different reference TEAR event rates in 500 subjects

Event Rate for Reference Product	Estimated 95% CI for the Event Rate (n=250)	Margin	Type I error 2 one-sided alpha	Power	Total N
5%	(2%,8%)	5.7%	0.05	80%	500
10%	(6%,14%)	7.9%	0.05	80%	500
15%	(11%,19%)	9.3%	0.05	80%	500
20%	(15%,25%)	10.5%	0.05	80%	500
25%	(20%,30%)	11.3%	0.05	80%	500
30%	(24%,36%)	12.0%	0.05	80%	500
35%	(29%,41%)	12.5%	0.05	80%	500
40%	(34%,46%)	12.8%	0.05	80%	500
45%	(39%,51%)	13.0%	0.05	80%	500
50%	(44%,56%)	13.1%	0.05	80%	500
55%	(49%,61%)	13.0%	0.05	80%	500
60%	(54%,66%)	12.8%	0.05	80%	500

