4 STUDY POPULATION

4.1 Study Population

A total of 500 subjects with T1DM are planned to be randomized in this study, to receive MYL-1601D or NovoLog® with a randomization ratio of 1:1.

A detailed description related to sample size determination is provided in [Section 7](#).

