5 SAMPLE SIZE AND POWER

Approximately 500 subjects with type 1 diabetes will participate in this trial. The sample size estimation is based on primary objective - to demonstrate that immunogenicity as assessed by TEAR rate with MYL-1601D is equivalent to that of NovoLog® during 24-week treatment. The 80% power will be achieved with 250 subjects per treatment arm to demonstrate that 90% confidence interval of treatment difference (MYL-1601D minus NovoLog®) is within prespecified \pm margin (Table 2 of the SAP) (Chow SC et al, 2002; Chow S-C et al 2003). The pre-specified equivalent margin is dependent on the final rate of NovoLog® TEAR rate. No replacement of subject will be performed if subject discontinued prematurely from the study.

Table 2: Margins and 95% CIs with different reference TEAR event rates in 500 subjects

Event Rate for Reference Product	Estimated 95% CI for the Event Rate (n=250)	Margin	Type I error 2 one-sided alpha	Power	Total N
5%	(2%,8%)	5.7%	0.05	80%	500
10%	(6%,14%)	7.9%	0.05	80%	500
15%	(11%,19%)	9.3%	0.05	80%	500
20%	(15%,25%)	10.5%	0.05	80%	500
25%	(20%,30%)	11.3%	0.05	80%	500
30%	(24%,36%)	12.0%	0.05	80%	500
35%	(29%,41%)	12.5%	0.05	80%	500
40%	(34%,46%)	12.8%	0.05	80%	500
45%	(39%,51%)	13.0%	0.05	80%	500
50%	(44%,56%)	13.1%	0.05	80%	500
55%	(49%,61%)	13.0%	0.05	80%	500
60%	(54%,66%)	12.8%	0.05	80%	500

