6.2 ITT analysis set

The ITT analysis set includes all randomized subjects without being in the site with GCP violation (including subjects who receive incorrect treatment, do not complete the study or do not comply with the protocol or used prohibited medication, randomized but do not take any study drug). The subjects who are in the site with GCP violation will be excluded from ITT analysis set.

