If the subject was ADA positive at baseline, then the imputed titer values will be used. The subject will be considered TEAR positive if the ADA titer at any post-baseline visit was $\geq 4\times$ the baseline titer. If none of the post-baseline titer values reached 4 times the baseline titer, then the subject will be classified as TEAR negative.

For each imputation, the proportion of responders, along with standard errors, will be estimated for each treatment group, and the estimate and standard error of the risk difference will be computed. These values will be combined across imputations using PROC MIANALYZE. Subsequently, the 90% confidence interval for the risk difference will be computed using the Wald confidence limit method.

An equivalence margin will be established as a function of the TEAR rate among the Novolog subjects. Under the null hypothesis of equivalence (i.e., $H_0: p_M = p_N$), the margin can be obtained as a function of the TEAR rate in the Novolog group using the following expression (Chow S-C et al., 2003, p. 91).

$$\delta = (z_\alpha + z_\beta) \sqrt{\frac{2p_N(1 - p_N)}{n_N}}$$

Selected values for δ are provided in Table 2 of Section 5 above. If the margin falls within the 90% confidence interval for the risk difference, then equivalence of MYL1601-D and Novolog will be declared.

These steps can be executed using code similar to the following:

```
proc freq data=simdata ;
title "90% Wald confidence interval";
by _imputation_;
ods output riskdiffcol2=rdiff1;
table group*resp / riskdiff (CL=WALD column=2) alpha=0.1;
weight count;
run;

data rdiff1; set rdiff1;
keep _imputation_ row risk ase lowercl uppercl;
if row='Difference';
run;

proc mianalyze data=rdiff1;
modeleffects risk;
stderr ase;
ods output ParameterEstimates=mirisk1;
run;

ods listing;
data parms1;
set mirisk1;
lowercl = estimate - (1.645*stderr);
uppercl = estimate + (1.645*stderr) ;
run;
proc print data=parms1;
var estimate stderr lowercl uppercl;
run;
```

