10.2 Tipping Point Analysis

The tipping point analysis will create a type of figure called a heat map. It will not impute data at the subject level, but rather will be based on the observed total counts of TEAR status and number of missing values per group.

The steps are summarised below:

For purposes of the code below, set

```
Nm = Total # of subjects randomized to MYL-1601D group
Nn = Total # of subjects randomized to Novolog group
Mm = # of subjects missing TEAR status in MYL-1601D
group
Mn = # of subjects missing TEAR status in Novolog group
TEARm = # of subjects in MYL-1601D group who are TEAR
positive
TEARn = # of subjects in Novolog group who are TEAR
positive
```

Then run code similar to the following. The code below assumes that the above variables have been created as global variables.

```
%macro heat;

data heatmap;
do i = 0 to &mn;
  do j = 0 to &mm;
    y = &tearn + i;
    x = &tearm + j;
    pn = y/&nn;
    pm = x/&nm;
    riskdiff = pm - pn;
    margin = (quantile('NORMAL',0.95) +
    quantile('NORMAL',0.90))*
    sqrt(2*pn*(1-pn)/&nn);
    output;
  end;
end;
run;

%do i = 0 %to &mn;
  %do j = 0 %to &mm;

    data imputed;
    length group $8;
    group="NOVOLOG";
    status=1;
    count=%eval(&tearn+&i);
    output;
    status=0;
    count=%eval(&nn - (&tearn+&i));
    output;
```

```

group="MYL-1601D";
status=1;
count=%eval(&tearm+&j);
output;
status=0;
count=%eval(&nm - (&tearm+&j));
output;
run;

ods exclude all;
proc freq data=imputed;
table group * status / riskdiff (cl=WALD column=2)
alpha=0.1;
weight count;
ods output riskdiffcol2=rdiff1;
run;
ods exclude none;
data ci;
set rdiff1 (where=(row="Difference"));
y = &tearn + &i;
x = &tearm + &j;
run;

data heatmap;
merge heatmap
ci (keep=x y risk ase lowercl uppercl)
;
by x y;
length color $8 digits $16 a1-a6 asterisk $1;
if -0.0000001 <riskdiff < 0.0000001 then do;
red=255;
green=255;
blue=255;
end;
else if riskdiff > 0 then do;
if riskdiff >= 0.16 then do;
red = round(484 - (1435*riskdiff));
green = 0;
blue = 0;
end;
else do;
red = 254;
green = round(255/(1+exp(-32.96*(0.1149-
abs(riskdiff)))));
blue = round(255/(1+exp(-21.58*(0.0793-
abs(riskdiff)))));

```

```

        end;
    else if . < riskdiff < 0 then do;
        red = round(255/ (1+exp(-18.51*(0.1108-
abs(riskdiff)))));
        green = round(255/ (1+exp(-27.85*(0.1699-
abs(riskdiff)))));
        blue = round(255/ (1+exp(-20.10*(0.1024-
abs(riskdiff)))));
    end;

    digits = "0123456789ABCDEF";

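### The 80% power in Protocol 7.1 is a complete-data figure; multiple imputation is not a valid reason for making no allowance for lost TEAR information

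*Protocol*

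**What the plan says.** Protocol 4.1 plans 500 randomized subjects, split equally between the two arms. Protocol 7.1 and SAP section 5 make the same power claim: "The 80% power will be achieved with 250 subjects per treatment arm to demonstrate that 90% confidence interval of treatment difference" lies inside the margin in Protocol Table 5 (SAP Table 2). Both rule out replacing subjects who stop early.

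On missing data, Protocol 7.1 adds: "An attrition rate is not considered; for the analysis an imputation of missing values will be done", and says that nobody will be left out of the primary analysis. SAP section 5 does not repeat that sentence, but adds no allowance either.

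The imputation is multiple imputation. Protocol 7.2.2 and SAP 7.2.1 and 8.7.2.1 derive TEAR status in each imputed data set, estimate the risk difference with a Wald standard error, and pool with PROC MIANALYZE.

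The margin is not one fixed number: "The pre-specified equivalent margin is dependent on the final rate of NovoLog® TEAR rate". SAP 8.7.2.1 gives a formula by which "the margin can be obtained as a function of the TEAR rate in the Novolog group", with the NovoLog sample size in the denominator.

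**The concern.** The protocol offers imputation as a substitute for a missing-data allowance. Multiple imputation can reduce bias and keeps every subject in the denominator, but it does not create observations. PROC MIANALYZE adds the between-imputation variance to the within-imputation variance, so the pooled interval is about as wide as the observed information warrants. If 250 per arm is just enough with complete data, any loss of TEAR information takes power below the stated 80%.

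At stake is a stated design property of the primary test. Someone interpreting a failed equivalence test needs to know how likely failure was with no true difference. If the power is believed to be 80% when it is lower, a shortfall in precision is easier to mistake for a difference between products.

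**Working it through.** **Inputs**
- 250 per arm, 80% power, 90% confidence interval (Protocol 7.1, SAP section 5).
- The Table 5 column "Type I error 2 one-sided alpha" is 0.05, so z(0.95) = 1.645.
- Margin formula from SAP 8.7.2.1: margin = (z_alpha + z_beta) × sqrt(2p(1 − p)/n_N), where p is the NovoLog TEAR rate and the true difference is zero.
- The code in SAP 10.2 shows the quantiles used: "margin = (quantile('NORMAL',0.95" plus the 0.90 normal quantile. So beta is halved for a two-sided equivalence test with 80% power, and the multiplier is 1.645 + 1.282 = 2.926.

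**Step 1: reproduce the plan's figure.** At p = 0.30 and n = 250, the margin is 2.926 × sqrt(2 × 0.30 × 0.70/250) = 2.926 × 0.0410 = 12.0%, as tabled. All 12 tabled margins agree with the formula to within 0.05 percentage points. Solving each row for n gives 247 to 253 per arm. Power at n = 250 is 79.5% to 80.6%, and the spread comes from rounding the margins. Without halving beta the requirement would be only 179 to 183 per arm, so that variant was not the one used. The table is correct, and 250 per arm is exactly the complete-data requirement.

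**Step 2: let a fraction f of the TEAR information be lost.** Imputed subjects stay in n_N, so the margin keeps its n = 250 value. The standard error grows by 1/sqrt(1 − f), which gives

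power = 2 × Phi[2.926 × sqrt(1 − f) − 1.645] − 1.

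**Step 3: check by simulation.** The simulation used 250 per arm, no true difference, TEAR status missing at random within arm and imputed from the same arm, 30 imputations, Rubin's rules, and estimate ± 1.645 standard errors. There were 20,000 trials at each of the reference rates 10%, 30% and 50%. Earlier visits were not used as predictors, so in the simulation f is the fraction of subjects with missing status.

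| f | Argument of Phi | Power by formula | Simulated, Table 5 margin | Simulated, margin recomputed from imputed NovoLog rate |
|---|---|---|---|---|
| 0 | 1.282 | 80.0% | 80.0–80.9% | 79.5–80.7% |
| 5% | 1.207 | 77.3% | 77.1–78.0% | 76.7–77.6% |
| 10% | 1.131 | 74.2% | 74.2–75.0% | 73.8–74.5% |
| 15% | 1.053 | 70.8% | 70.5–71.0% | 70.1–70.7% |
| 20% | 0.973 | 66.9% | 66.7–67.4% | 66.3–67.0% |

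At f = 2% the formula gives 78.9%. Power is more than 2 points below 80% once about 3.8% of the information is lost.

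**The case against.** **Dropout is not information loss.** This is the strongest counter-argument, and it stands. TEAR is met at any post-baseline visit, and there are seven such samples (Visits 8 to 13 and 15). A subject already TEAR positive is not missing (SAP 7.2.1). Subjects who stop treatment are asked to continue the scheduled visits, and their data enter the primary analysis (Protocol 4.2.3 and 7.2.2). Those who leave the study are due an early termination visit with an antibody sample (Protocol 6.3.4). The imputation models use each subject's earlier visits (SAP 8.7.2.1).

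A reader might therefore infer that 10% dropout means 74% power. The documents do not support that. As an illustration, assume 10% dropout spread evenly over the seven visits and no retrieved data. The information loss is then roughly 7% if antibody onset is uniform and 4% to 5% if it is early, for power of about 76% and 78%. The effect can also go the other way: with as few as six retrieved dropouts per arm, missing values are modelled from that subgroup alone, which could lose more.

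**Site exclusion.** SAP 6.2 says: "The subjects who are in the site with GCP violation will be excluded from ITT analysis set". A reader might infer that this lowers power further. That is not established. Removed subjects, unlike imputed ones, leave n_N, and the SAP 8.7.2.1 margin scales with 1/sqrt(n_N). With equal losses from both arms, margin and standard error grow together. At p = 0.30 the margin is 12.0%, 12.2% and 12.6% for n = 250, 240 and 225, and nominal power stays at 80%. The label in the SAP 10.2 code refers to subjects randomized, but the same count is the denominator of the NovoLog rate, so it has to match the analysed set. The exclusion does mean that the Protocol 7.1 statement that nobody is left out no longer describes the plan.

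**The analysis itself is sound on this point.** A reader might infer that the plan analyses imputed values as if observed, or that false equivalence becomes more likely. Pooling with PROC MIANALYZE carries the extra variance into the interval, and lower power of this kind does not raise the risk of a false claim of equivalence. Only the planning statement is at fault.

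**Conclusion.** The concern holds as a fault in the planning rationale, not in the Table 5 arithmetic. Imputation is not a valid reason for ignoring missing data, and 80% is the power with 250 fully observed subjects per arm. Power falls below that whenever TEAR information is lost: by about 1 point at 2% loss, 3 points at 5%, 6 points at 10%, 9 points at 15% and 13 points at 20%.

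These sizes assume no true difference, equal fractional loss in both arms, and a margin based on 250 per arm. The documents state no expected missing-data rate, so they do not show how large the shortfall is in this trial. It may be small.

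**What to change.** 1. In Protocol 7.1, delete the argument that imputation makes an attrition allowance unnecessary.
2. In Protocol 7.1 and SAP section 5, state that 80% is the power with complete TEAR data on 250 subjects per arm. Add that it is about 77%, 74%, 71% and 67% at 5%, 10%, 15% and 20% loss of TEAR information, with the margin based on 250 per arm.
3. Say beside those figures that they refer to lost information and not raw dropout, and that no missing-data rate was assumed. Note that the loss will usually be smaller than raw dropout, because early positives, continued off-treatment visits and earlier samples contribute. Note also that imputing from a small retrieved-dropout subgroup could lose more.
4. Bring the Protocol 7.1 statement that nobody is excluded from the primary analysis into line with SAP 6.2.

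The cost is a few sentences and a slightly less favourable power statement. No extra patients are needed, and the endpoint, margin rule, imputation and decision rule stay as they are.
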